STUDY PROTOCOL

Nasal Intubation Using King Vision Video Laryngoscopy

[name]

(NCT03126344)

April 27, 2017

STUDY PROTOCOL

Title: A randomized controlled comparison of non-channeled King Vision, McGrath MAC video laryngoscope and Macintosh direct laryngoscope for nasotracheal intubation in patients with predicted difficult intubations.

Background: King Vision and McGrath MAC video laryngoscopes (VLs) are increasingly used. However, it remains unclear whether non-channeled King Vision or McGrath MAC VL, compared with conventional laryngoscope, provide shorter intubation time and a higher first success rate for NTI when used by experienced provider in management of predicted difficult intubation. It is also unclear whether non-channeled King Vision VL is superior to McGrath MAC VL when used for NTI.

Objective: To evaluate the performance of nasotracheal intubation in patients with predicted difficult intubations using non-channeled King Vision VL, McGrath MAC VL or Macintosh laryngoscope by experienced intubators.

Study Design: A single blind, three parallel arms, randomized controlled trial comparing NTIs using non-channeled King Vision VL, McGrath MAC VL and Macintosh DL in adults with predictors of difficult airways.

Subjects: Consecutive patients, between 18 and 60 years old with American Society of Anesthesiologists (ASA) classification of I or II, and requiring NTI for elective oral and maxillofacial surgery, were screened in the Preoperative Evaluation Unit of our institute.

Sample size: Based on the analysis of power analysis software, we take the type I error α as 0.05, the expected effect is 0.8, and the ideal test efficacy level is 0.8, then the minimum sample size of each group is 26. In order to reduce the loss of follow-up error, add 20% on this basis, then each group needs about 30 cases.

Recruitment method: Inpatients

Inclusion criteria: EGRI score 1–7.

Exclusion criteria: EGRI score > 7, history of reflux or diagnosed oesophageal disease, severe obstructive sleep apnea (OSA) and morbid obesity (body mass index > 40 kg/m²)

Study Methods:

1. Determine the subjects: select the patients who need nasotracheal intubation for elective operation, and determine 90 subjects strictly according to the inclusion and exclusion criteria, 30 in each group.

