2. Group: Patients were randomly assigned to King Vision group, McGrath group or Macintosh group via a computer-generated randomization table: King Vision video laryngoscope group (group K, n = 30), McGrath MAC video laryngoscope group (group M1, n = 30) and Macintosh laryngoscope group (group M2, n = 30).

3. Anesthetic methods: the anesthetic methods of three groups were the same. Patients were asked which nostril was clearer. If both sides were equal and the surgeon had no objection, the right nostril was chosen.

No premedication was administered. Lactated Ringer's solution infusion was started intravenously to deal with the fluid loss from the overnight fast after entering the operating theatre. A standard preparation was then performed, including heart rate (HR), lead II ECG, SpO₂ (pulse oximetry), and end expiratory carbon dioxide. A Bispectral (BIS) index sensor was attached to the patient's forehead in conjunction with the BIS Monitor. Cannulation of right radial artery was performed under local anesthesia for invasive blood pressure monitoring.

All patients were preoxygenated by a facemask in the position of neutral. Prior to anesthesia induction, the nasal mucosa was well prepared with 1% tetracaine hydrochloride jelly for 2 min and five drops of ephedrine hydrochloride nitrofurazone (containing approximately 2 mg ephedrine) in all patients. Baseline hemodynamic data were recorded by an investigator after a stabilization period of 10 min.

The nasotracheal tube used was reinforced endotracheal tube (ETT, Safety-Flex with Murphy Eye, oral/nasal, Athlone, Ireland; ID 6.5mm in female and ID 7.0mm in male patients) and was well lubricated with 1 % tetracaine hydrochloride jelly. Dosing of induction medications was given at the discretion of the attending anesthesiologists. Induction agents included midazolam (0.02 mg/kg), propofol (1.5~2 mg/kg) and fentanyl (2 µg/kg). Upon loss of consciousness and jaw relaxation, manual ventilation was tested. If manual ventilation was available, cisatracurium besilate (0.15 mg/kg) was administered and post induction values were recorded 3 min after induction. Unsuccessful manual ventilation led to study exclusion.

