The anesthesiologist tried to intubate when the Train of Four (TOF) count reached zero and BIS value decreased to 50. NTI was performed in a standard manner. First, a preformed ETT was inserted into the nostril and advanced to the posterior nasopharyngeal wall. Second, a laryngoscope blade was introduced into the mouth to expose the glottis. If it's necessary, the BURP maneuver (backward, upward, right-sided pressure) on the thyroid cartilage was attempted to obtain good glottis visibility. And ultimately, the ETT was inserted into the trachea with the aid of Magill's forceps, head flexion, or cuff inflation if necessary.

4. Observation outcome:

(1) Primary outcome: the intubation time

(2) Secondary outcome measures included time to expose the glottis (laryngoscopy time) and the view of glottis opening valued by Cormack-Lehane grade. A Cormack-Lehane grade IV was defined as laryngoscopy failure. A blinded investigator also recorded the hemodynamic changes (MAP, HR) during the procedure of NTI. The maximum values of invasive MAP were recorded. After successful intubation, the subjective sensation of the intubator (ease of device insertion, quality of view on display and ease of tube advancement) was graded as excellent, good, fair and poor. Other intubation parameters included incidences of bleeding or dental injury, number of assist maneuvers (use of BURP maneuver, Magill's forceps, or cuff inflation). Twenty-four hours after the procedure, a nurse anesthetist blinded to group assignment recorded the severity of sore throat and hoarseness.

Statistical analysis

Our sample size estimation was based on previous studies (11,23), in which the standard

deviations (SD) of intubation time were estimated as 8 and 13.7 seconds. To detect a intergroup difference of 10 seconds in intubation time with α of 0.05 and β of 0.8, we estimated that 30 patients would be enough for each group. To compensate for patients dropping out during the study, additional patients (10%) were added. The final sample size of 33 patients was in each group.

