Mean (SD) or Median (IQR [range]) was used to describe the parametric data. The number (percentage) was used to describe nonparametric data. Statistical analyses were performed with Prism 5.0 for Windows (GraphPad Software, Inc., La Jolla, California, USA). Binary data for three groups were analyzed using chi-square test and each two groups were compared with chi-square segmentation method or Fisher's exact test as appropriate. One-way analysis of variance (ANOVA) with post-hoc Bonferroni's Multiple Comparison test was used to analyze parameter data for changes within groups. The Kruskal-Wallis ANOVA with post-hoc Dunn's test was used to analyze ordinal data. A p value less than 0.05 was considered as significant.

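### The intubator's ease-of-use ratings are tied to successful intubation, and the plan does not say what is recorded or analysed when the assigned laryngoscope fails

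*Combined protocol and SAP*

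**What the plan says.** Section 4 (Observation outcome), item (2), introduces the operator ratings with "After successful intubation, the subjective sensation of the intubator (ease of device insertion, quality of view on display and ease of tube advancement) was graded". The scale has four levels ("was graded as excellent, good, fair and poor"), none of them for failure. The ratings are secondary; the primary outcome is intubation time.

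The same item defines one kind of failure: "A Cormack-Lehane grade IV was defined as laryngoscopy failure". It does not link that definition to the ratings. Failed intubation, number of attempts and change of device are neither defined nor listed as outcomes, although the Background asks whether the video laryngoscopes "provide shorter intubation time and a higher first success rate for NTI".

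The only exclusion stated during the procedure is in Study Methods, item 3 (Anesthetic methods): "Unsuccessful manual ventilation led to study exclusion". That test comes before laryngoscopy, so it does not cover a failed intubation.

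For the analysis, the Statistical analysis section says "The Kruskal-Wallis ANOVA with post-hoc Dunn's test was used to analyze ordinal data". It names no analysis set and gives no rule for a missing rating.

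**The concern.** Success of intubation happens after randomization and can depend on the device. A rating that exists only for successes compares selected subsets of the arms, and the patients left out are those in whom the device did worst. A rating that exists for everyone but may describe a rescue device is not a rating of the assigned device. The sentence allows both, and nothing elsewhere in the plan settles which applies.

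What is at stake is the ease-of-use comparison. The population was chosen for predicted difficulty, so any failures are the patients in whom these ratings would say most. Success rate and device changes are not among the listed outcomes, so a reader of the results could not rebuild the denominators from what the plan undertakes to report.

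**Working it through.** **Plan's own figures.** The documents give no number for the ratings or for failed intubations, so there is no plan figure to reproduce on this point. The arm size used below is 30 (Study Methods, item 2). It agrees with the Statistical analysis section before dropout: for a 10-second difference, SD 13.7, two-sided α of 0.05 and power 0.8 (the section's β of 0.8 read as power), n = 2 × (1.960 + 0.842)² × 13.7² / 10² = 29.5, so 30. That section then adds 10% to reach 33, which is covered at the end.

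**What each reading implies for the ratings**

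| Situation | Read as a condition | Read as timing |
|---|---|---|
| Intubated with the assigned device, first or later attempt | Graded | Graded |
| Assigned device fails, airway secured with another device | No grade for the assigned device | Graded, but the device described is not specified |
| No successful intubation | No grade | No grade |

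The gap concerns only failure of the assigned device. A failed first attempt later solved with the same device loses nothing.

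**Size if failures go unrated.** The inputs are assumptions, because the documents give no failure rate and no rating distribution. Rated patients in every arm are poor/fair/good/excellent in 10/20/30/40%, scored 1 to 4. One arm has f failures in 30 and the other two have none.

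- Failures left out: good or excellent = 30% + 40% = 70% for any f. Mean score = 0.1×1 + 0.2×2 + 0.3×3 + 0.4×4 = 3.00.
- Failures counted as poor: good or excellent = 0.70 × (30 − f)/30. Mean score = [3.00 × (30 − f) + 1 × f]/30.
- Overstatement from leaving them out = 0.70 × f/30.

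| f of 30 | Good or excellent, left out | Good or excellent, counted | Overstatement (points) | Mean, left out | Mean, counted |
|---|---|---|---|---|---|
| 0 | 70% | 70.0% | 0 | 3.00 | 3.00 |
| 1 | 70% | 67.7% | 2.3 | 3.00 | 2.93 |
| 3 | 70% | 63.0% | 7.0 | 3.00 | 2.80 |
| 6 | 70% | 56.0% | 14.0 | 3.00 | 2.60 |

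**Effect on the planned test.** Three-arm Kruskal-Wallis test at 0.05, 3,000 simulated trials per row, same assumptions:

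| f of 30 | Rejection, failures left out | Rejection, failures counted |
|---|---|---|
| 0 | 5.3% | 5.3% |
| 1 | 4.7% | 4.2% |
| 3 | 4.8% | 8.4% |
| 6 | 5.0% | 20.2% |

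Simulation error near 5% is about √(0.05 × 0.95/3000) = 0.4 percentage points. With failures left out the test cannot see them. With failures counted it begins to respond at about 3 in 30 and is still weak at 6.

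**With 33 per arm.** The overstatement is 0.70 × f/33 = 2.1, 6.4 and 12.7 points for f = 1, 3 and 6. The choice between 30 and 33 does not change the conclusion.

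**The case against.** The strongest reply is that the opening phrase is about timing. The paragraph runs in time order, ending with an assessment at twenty-four hours, and it is natural for an operator to complete a rating once the airway is secure. Nothing says that failed patients are unrated or excluded. This is fair. It means that a reader who infers that such patients are removed goes beyond the text. It does not close the gap, because under that reading the plan still does not say which device the grade describes after a change of device.

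A second reply is that complete failures may be few or absent: the operators are experienced, patients with EGRI above 7 are excluded, and several assist maneuvers are allowed. This also stands. With no failures the effect is zero.

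A reader might infer that the worse device will come out looking better than its competitors. The documents do not support that. It would need failures that differ between arms, and the plan states no failure rate and no expected difference. Even in the illustration the failing device comes out level with the others, not ahead: it looks better than it should, which is a weaker statement.

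A third reply is that little would change. With 1 to 3 failures the planned test moves only slightly, the ratings are unblinded operator opinion, and Cormack-Lehane grade is collected without the success condition, so the worst views remain visible. All of that limits the importance. Failed tube advancement, however, is not captured by any listed outcome.

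Finally, scoring failures as poor mixes perception with an objective event. That is a real cost, which separate failure counts make visible.

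**Conclusion.** The point holds as a gap in how the ratings are defined and analysed. The plan ties them to success, which the device can influence, and gives no rule for failure of the assigned laryngoscope. If failures are more frequent with one device, its ratings can be too favourable; if there are none, or they are equal across arms, the comparison need not shift.

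The actual size cannot be known from the documents. The range of 0 to 14 percentage points rests on three assumptions: the 10/20/30/40% distribution, failures confined to one arm, and failures left unrated. It does not measure the misattribution that could arise under the timing reading. The matter affects one set of secondary, subjective outcomes and leaves the primary outcome definition untouched. It is worth correcting because the correction is cheap and works under both readings.

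**What to change.** In section 4, item (2), replace the opening condition with: *after the last attempt with the assigned laryngoscope, whether or not intubation succeeded*. State that the grade refers to the assigned device only. The last attempt is a better anchor than the first, since it keeps the operator's full experience with the device. This wording sets no rule on the number of attempts or on changing device; it only fixes what is recorded.

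In the Statistical analysis section, add that:

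- the ratings are analysed in every randomized patient in whom the assigned device was used;
- failure to insert the blade, or to place the tube, with the assigned device takes the worst category for that item;
- failures are reported by arm next to the ratings;
- a sensitivity analysis is limited to patients intubated with the assigned device.

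The cost is a few sentences in the protocol and a change to the rating form, with no added visits or staff. The downside is that the worst category then combines operator opinion with objective failure; the failure counts and the sensitivity analysis let a reader separate the two.

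### Head flexion is one of four permitted intubation aids but is missing from the assist-manoeuvre outcome, so its use is uncounted or unreported, with unknown effect on the device comparison

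*Combined protocol and SAP*

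**What the plan says.** Study Methods, item 3 (Anesthetic methods), describes the procedure in two steps. For exposing the glottis, where needed, "the BURP maneuver (backward, upward, right-sided pressure) on the thyroid cartilage was attempted to obtain good glottis visibility". For passing the tube, "the ETT was inserted into the trachea with the aid of Magill's forceps, head flexion, or cuff inflation if necessary". That makes four aids in all, each used only when needed.

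Item 4 (Observation outcome), part (2), lists the secondary measures. A late sentence in that list opens "Other intubation parameters included incidences of bleeding or dental injury" and goes on to "number of assist maneuvers (use of BURP maneuver, Magill's forceps, or cuff inflation". Three of the four aids are named. Head flexion appears once in the document, in the procedure, and in no outcome. Nothing says that it is recorded elsewhere, that every patient receives it, or that the bracketed list is only a set of examples.

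The primary measure is separate: "Primary outcome: the intubation time".

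**The concern.** The objective is to compare how nasotracheal intubation performs with three laryngoscopes, and how often the operator needs help is a direct measure of that. Magill's forceps, head flexion and cuff inflation are offered as alternatives for the same step, with no rule for choosing among them. Two of the three are counted.

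The operator knows which device is in hand, because the intubator cannot be blinded to it. If operators turn to head flexion more often with one device, that device will appear to need less help than it did. If they use it to a similar degree with all three, the need for help is understated throughout. At stake is the interpretation of one secondary parameter, not the trial's main result.

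**Working it through.** **Step 1. Compare the two lists.** The plan gives no figure for this parameter, so there is none to reproduce. The check starts from the text.

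| Aid | Permitted (item 3) | Counted (item 4, part 2) |
|---|---|---|
| BURP | yes | yes |
| Magill's forceps | yes | yes |
| Head flexion | yes | no |
| Cuff inflation | yes | yes |

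**Step 2. Effect on one patient, if the parameter is a total.**
- Head flexion only: recorded 0, the same as a patient who needed no aid; actual 1.
- Head flexion plus one other aid: recorded 1; actual 2.

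If each aid is tabulated separately, the three named rates are right and the fourth is absent.

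**Step 3. Direction of the effect on a two-arm difference.** Take any assistance yes/no, with assumed true need of 70% and 35% (difference 35 points).
- Same share *s* of assisted cases missed in each arm: measured difference = 35 × (1 − *s*). For *s* = 10% it is 31.5 points; for *s* = 40% it is 21 points. It shrinks.
- Same number of percentage points missed, say 10 in each arm: 60% − 25% = 35 points. It is unchanged.
- More missed in the lower-need arm, say 5 and 15 points: 65% − 20% = 45 points. It widens.
- More missed in the higher-need arm, say 15 and 5 points: 55% − 30% = 25 points. It shrinks.

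The direction therefore depends on rates that the documents do not give.

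**Step 4. Can it create a difference?** Assumptions, none of them from the documents except the 30 per arm: true need 60% in both arms; head-flexion-only makes up 10% of assisted cases in one arm and 30% to 40% in the other.

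Measured rate = true rate × (1 − head-flexion-only share):
- 0.60 × 0.90 = 54%
- 0.60 × 0.70 = 42%
- 0.60 × 0.60 = 36%

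With 30 × 0.60 = 18 assisted patients per arm, this misses 18 × 0.10 = 1.8 patients in one arm and 5.4 to 7.2 in the other.

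The chance of a significant result is the sum, over all pairs of counts (*a*, *b*) for which the test gives p < 0.05, of Bin(*a*; 30, p₁) × Bin(*b*; 30, p₂).

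| Two-arm test at 0.05 | 60% v 60%, nothing missed | 54% v 42% | 54% v 36% |
|---|---|---|---|
| Uncorrected chi-square | 4.9% | 15.7% | 29.3% |
| Fisher's exact | 2.6% | 10.1% | 20.9% |

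If the pairwise chi-square tests are instead run at 0.05/3, the false-difference range is 6–15%.

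**The case against.** **The outcome need not be a total.** The document never defines an assisted/unassisted endpoint, and the brackets could mean that the use of each named aid is reported separately. On that reading nobody is misclassified. This stands in part. A reader might infer that a head-flexion-only patient is certain to be scored as needing no help; that follows only if a total or a composite is used. The wording does speak of a number of manoeuvres, however, and with separate rates one of three interchangeable aids for passing the tube still goes unreported.

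**The choice of aids to tabulate is a matter of scope, or the list is illustrative.** Nothing in the brackets marks the list as examples, and someone completing a case form would treat it as the definition. The procedure puts head flexion in the same phrase and under the same condition as two aids that are counted, "with the aid of Magill's forceps, head flexion, or cuff inflation if necessary", and gives no reason to treat it differently.

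**Undercounting does not always shrink a difference.** This stands in full. A reader might infer that the omission makes the trial conservative, or that it biases the comparison towards a particular device. Step 3 shows that the gap can shrink, stay the same or widen, and the documents cannot say which applies.

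**The illustration is only that.** This also stands. It uses assumed rates, a yes/no endpoint and one two-arm comparison. The Statistical analysis section gives binary data a three-group chi-square test, followed by pairwise segmentation or Fisher's exact test, and it states a final size of 33 per arm rather than 30. The larger shares drive the larger figures. No power is claimed for this parameter.

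**Difficulty is partly captured elsewhere.** Intubation time and the operator's grading of tube advancement are recorded whichever aid is used. That lessens the loss, but neither measure shows which aid was needed.

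**Conclusion.** The point holds as an inconsistency between two lists, with a definite effect on what is recorded and an unknown effect on the comparison. Head flexion is a permitted aid that the outcome does not count. Its use is lost from a total, or missing from a table of separate aids.

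Whether this matters to the device comparison depends on how often head flexion alone is used in each arm, and the documents are silent on that. The illustrative false-difference rates of 16–29% (uncorrected chi-square) or 10–21% (Fisher's exact) hold only for the assumed 60% need and the assumed 10% against 30–40% shares. They show that unequal use could mislead, not that it will.

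A reader should not carry the point over to the main result. Intubation time and the sample size do not depend on this parameter. It is a minor correction, worth making because it costs almost nothing.

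**What to change.** Define the parameter as the number of assist manoeuvres among BURP, Magill's forceps, head flexion and cuff inflation. Record each one on the case form, and report each aid by arm as well as the total. Separate reporting lets a reader see whether operators favoured different aids with different devices.

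If head flexion was left out on purpose, the plan should at least say why, although its use would then remain unreported.

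The cost is one extra case-form item and two words in the outcome definition. Randomisation, sample size and clinical management do not change, nor do the aids that are permitted. The item should be on the form before data are collected, since use that is not noted at the time may not be recoverable.

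### If the SD is 13.7 s, the stated 80% power does not describe the planned Bonferroni pairwise tests: a given device pair has about 65% power (30 evaluable per group) or 70% (33)

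*Combined protocol and SAP*

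**What the plan says.** The primary outcome is intubation time. The sample-size paragraph under Statistical analysis draws on earlier studies in which the SDs "of intubation time were estimated as 8 and 13.7 seconds". It sets the target as "To detect a intergroup difference of 10 seconds in intubation time with α of 0.05 and β of 0.8" and concludes that "we estimated that 30 patients would be enough for each group". A 10% dropout allowance follows: "The final sample size of 33 patients was in each group". The paragraph does not say which SD was used, names no test and mentions no multiplicity adjustment.

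For the analysis, the same section specifies "One-way analysis of variance (ANOVA) with post-hoc Bonferroni" comparisons, a method that "was used to analyze parameter data for changes within groups".

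The Background frames the questions by pairs of devices: "it remains unclear whether non-channeled King Vision or McGrath MAC VL, compared with conventional laryngoscope, provide shorter intubation time", and "It is also unclear whether non-channeled King Vision VL is superior to McGrath MAC VL when used for NTI".

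The Sample size paragraph near the start of the protocol holds a separate calculation: α 0.05, an effect of 0.8 and power 0.8 give at least 26 per group, raised to about 30. Study Methods, items 1 and 2, also use 30 per group, 90 in total.

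**The concern.** Three arms give three pairs, so a Bonferroni correction tests each pair at 0.05/3, about 0.0167. If the 30 per group came from a single comparison at 0.05, the 80% belongs to a more lenient test than the one that will say which device is faster.

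What is at stake is how a non-significant pair is read. Someone who takes 80% as the power for each pair could treat a non-significant result, for instance King Vision against McGrath, as evidence of no difference. At 65% power, a true 10 s difference in that pair would be missed about one time in three.

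**Working it through.** **Inputs.** Difference 10 s, α 0.05, the two SDs, and 30 and 33 per group, all from the sample-size paragraph under Statistical analysis. That paragraph gives 0.8 as β; I read it as power, as in the earlier Sample size paragraph. Two-sided testing is assumed. Bonferroni over three pairs comes from the analysis paragraph and the Background questions.

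**1. Reproducing the plan's 30.** Normal formula for two means: n = 2(1.96 + 0.842)² × SD² / 10² per group.

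| SD (s) | Formula result | n per group |
|---|---|---|
| 8 | 10.05 | 11 |
| 10.85 (mean of the two) | 18.5 | 19 |
| 11.2 (root mean square) | 19.8 | 20 |
| 13.7 | 29.5 | 30 |

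Only 13.7 s gives 30; a one-sided test at 13.7 s gives 24. The unadjusted two-sample t-test with 30 per group and SD 13.7 s has 79.4% power, which agrees with the stated 80%. One rival comes close: a three-group F-test at SD 13.7 s with means 0/0/10 needs 29.

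**2. Power of the planned pairwise test.** Noncentral t with pooled ANOVA error, 3(n − 1) degrees of freedom, two-sided 0.05/3, SD 13.7 s. Noncentrality = 10 / (13.7 × √(2/n)).

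| n per group | Noncentrality | df | Critical t | Power | Difference with 80% power |
|---|---|---|---|---|---|
| 30 | 2.83 | 87 | 2.44 | 65.0% | 11.6 s |
| 33 | 2.96 | 96 | 2.44 | 70.1% | 11.1 s |

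Requiring a significant F-test first changes these powers by less than half a point (200,000 simulated trials). Reaching 80% in an adjusted pair at SD 13.7 s takes 41 evaluable per group. The 33 includes the dropout allowance, so 30 evaluable is the planned case.

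**3. Dependence on the SD** (same test, 10 s difference).

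| SD (s) | Power, n = 30 | Power, n = 33 |
|---|---|---|
| 8 | 99% | 99.5% |
| 10.85 | 87% | 90% |
| 11.2 | 84% | 88% |
| 13.7 | 65% | 70% |

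Power equals 80% at an SD of 11.8 s (n = 30) or 12.4 s (n = 33).

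**4. Other meanings of the 80%, at SD 13.7 s.**

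| Criterion | n = 30 | n = 33 |
|---|---|---|
| Given pair, Bonferroni over only the two video-versus-Macintosh pairs | 71% | 75% |
| F-test, means 0/0/10 | 83% | 86% |
| F-test, means 0/5/10 | 70% | 75% |
| Both video arms save 10 s: at least one pair against Macintosh significant | 80% | 84% |
| Both video arms save 10 s: both pairs significant | 50% | 56% |

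The last two rows are simulated (400,000 trials, Bonferroni over three pairs).

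**5. The earlier Sample size paragraph.** If its effect of 0.8 is a standardised difference, an unadjusted two-sample t-test needs exactly its 26 per group (power 80.7%). At 0.05/3 with pooled error, power for a pair is 67% with 26 and 74% with 30. No SD is needed for this result.

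**The case against.** The strongest reply is that the documents never select 13.7 s. Of the four SD values tried, only the largest produces a shortfall. Nor does reproducing 30 settle how the trial was sized. An F-test at SD 13.7 s with means 0/0/10 needs 29, and that test is part of the planned ANOVA. An adjusted pair at SD 11.2 s needs 28, which fits a claim that 30 would be enough. On either reading, sizing and analysis agree. The plan also never promises 80% for each pair: the pairwise questions stand in the Background, while the Objective speaks only of evaluating the devices. Finally, the Bonferroni test is assigned to changes within groups, which would suit the repeated haemodynamic measurements.

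Much of this stands as a limit on certainty. The SD, the sizing test and the number of corrected pairs are all inferred, so the finding is conditional. It does not remove the point. A smaller SD does not give 30 by the unadjusted formula, and if one was used the plan needs to say so. A significant F-test does not show which device is faster, which is what the Background asks. Intubation time is measured once per patient and no other test for continuous data is named, so the between-group reading is the natural one. Correcting for two pairs still leaves 71% or 75%. The earlier Sample size paragraph also falls below 80% per pair without any SD, provided its 0.8 is a pairwise standardised difference.

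**Conclusion.** The concern holds, on condition that the SD is 13.7 s. No sum in the plan is wrong and Type I error is unaffected. On the SD that best reproduces the plan's own 30, the planned Bonferroni tests give about 65% power for a 10 s difference in a given pair with 30 evaluable per group, or 70% with 33 if nobody drops out.

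This assumes a common SD, two-sided tests, correction over three pairs, and ANOVA with Bonferroni as the between-group test of intubation time. With an SD of 11.8 s or less (n = 30), or 12.4 s or less (n = 33), the shortfall disappears. The 80% can also stand as a description of a weaker criterion, such as the F-test for means 0/0/10. The conflict between 30 and 33 per group is separate and needs no assumption about the SD.

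**What to change.** Keep the planned tests and restate the sample-size paragraph under Statistical analysis, naming the SD, the test and the α level. If 13.7 s was used, for example:

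> *With 30 evaluable patients per group, SD 13.7 s and Bonferroni-corrected pairwise tests (two-sided 0.05/3), power for a 10 s difference in intubation time in a given pair is about 65%; the difference detectable with 80% power is about 11.6 s.*

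With 33 evaluable per group the figures are 70% and 11.1 s. If a smaller SD was used, give it and the matching power. If the 80% was meant for the F-test or for at least one significant pair, say so.

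In the analysis paragraph, state that ANOVA with Bonferroni is the between-group test of intubation time, and list the pairs it covers. Reconcile the 30 per group in Sample size and Study Methods with the 33 in Statistical analysis.

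The cost is rewording only: no extra patients and no change of test. The price is a less favourable stated per-pair power if the SD is 13.7 s.

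### Two sample-size targets that cannot both stand: 30 per arm (90) with the loss allowance already included, and 33 per arm (99 implied) with 30 as the number before dropout

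*Combined protocol and SAP*

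**What the plan says.** The Sample size entry near the start of the protocol takes alpha 0.05, an expected effect of 0.8 (no unit) and power 0.8, and states "then the minimum sample size of each group is 26". For loss to follow-up it says "add 20% on this basis, then each group needs about 30 cases". Study Methods, item 1, then instructs the team to "determine 90 subjects strictly according to the inclusion and exclusion criteria, 30 in each group". Item 2 repeats n = 30 for each of the three randomised groups.

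The Statistical analysis section has a second calculation. It cites SDs of 8 and 13.7 seconds for intubation time and a 10-second difference between groups, "with α of 0.05 and β of 0.8", and reports that "we estimated that 30 patients would be enough for each group". It continues: "To compensate for patients dropping out during the study, additional patients (10%) were added". It ends: "The final sample size of 33 patients was in each group". It gives no total; 3 × 33 = 99.

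Neither section refers to the other.

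**The concern.** The number 30 does two incompatible jobs. In the Sample size entry it is the number to enrol, with loss already allowed for. In Statistical analysis it is the number needed before any loss, and 33 is the number to enrol. The two calculations also assume different effects (0.8 against 10/13.7 = 0.73) and different loss allowances (20% against 10%).

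The recruitment target is a core design figure. While both numbers stand, nobody can tell whether stopping at 90 is on target or early, and either stopping point could be justified afterwards. Both calculations expect some loss, and the plan does not say whether lost patients are replaced. If 30 per arm are randomised, any unreplaced loss leaves fewer than the 30 that Statistical analysis says are needed.

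**Working it through.** **Assumptions.** The plan does not state sidedness or the test behind either calculation. I take a two-sided, two-sample comparison of means for one pair of arms, and read the effect of 0.8 as a standardised difference and the stated β of 0.8 as power 0.8.

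**Formula.** With the normal approximation, n per arm = 2(z₁₋α/₂ + z₁₋β)² / d², where d = difference/SD. At alpha 0.05 and power 0.8 the numerator is 2 × (1.960 + 0.842)² ≈ 15.70. The t-test figures use the noncentral t distribution.

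**Reproducing the plan's base figures.**

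| Source | d | Normal approximation | t-test |
|---|---|---|---|
| Sample size entry | 0.8 | 15.70/0.64 = 24.53, so 25 | 25.52, so 26 |
| Statistical analysis, SD 13.7 s | 10/13.7 = 0.730 | 29.46, so 30 | 30.45, so 31 |
| Statistical analysis, SD 8 s | 10/8 = 1.25 | 10.05, so 11 | 11.09, so 12 |

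The 26 is reproduced by the t-test. The 30 is reproduced by SD 13.7 s with the normal approximation. SD 8 s does not give 30, and neither does combining the two SDs as √((8² + 13.7²)/2) ≈ 11.2 s, which gives 20. The plan does not say that 13.7 s was the SD used.

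**Loss allowances.**
- Statistical analysis: 30 × 1.10 = 33, as stated.
- Sample size entry: 26 × 1.20 = 31.2, which is not 30. The step from 26 to 30 is 30/26 = 1.154, about 15%.

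**Targets.** 3 × 30 = 90 and 3 × 33 = 99, a gap of 3 per arm and 9 in total.

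**Evaluable numbers at 10% loss.** 30 × 0.9 = 27; 33 × 0.9 = 29.7, about 30.

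**Power for one pairwise comparison.**

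| Evaluable per arm | SD 13.7 s, alpha 0.05 | SD 13.7 s, alpha 0.05/3 | d = 0.8, alpha 0.05 | d = 0.8, alpha 0.05/3 |
|---|---|---|---|---|
| 27 | 74.9% | 58.5% | 82.2% | 67.9% |
| 30 | 79.4% | 64.2% | 86.1% | 73.5% |
| 33 | 83.2% | 69.3% | 89.3% | 78.3% |

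At SD 8 s, 27 per arm gives 99.5% at alpha 0.05 and 98.1% at 0.05/3.

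At SD 13.7 s the conflict costs 79.4 − 74.9 = 4.5 points unadjusted and 64.2 − 58.5 = 5.7 points at 0.05/3. Both alphas are shown because the plan names a post-hoc Bonferroni test but attaches it to within-group changes, so it is unclear whether it applies to the comparison of intubation time between arms.

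**The case against.** The best attempt at reconciliation is to read 33 as enrolled and 30 as evaluable. It fails: the 30 in the Sample size entry already contains a loss allowance, and Study Methods attaches n = 30 to the randomised groups.

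A better argument is that the operational instructions agree with each other on 90 and 30 per arm, and only the justification paragraph says 33. That makes 30 the more natural reading but does not settle the matter, because the paragraph calls 33 final.

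It can also be said that the consequences are small. The gap is nine patients. Under the Sample size entry's own effect of 0.8, 27 evaluable per arm still gives 82% unadjusted. Intubation time is measured during the procedure, so loss may be below 10% for the primary outcome; the visible route is exclusion after failed manual ventilation, and a failed intubation might also yield no time. With no loss, 30 per arm gives 79% at SD 13.7 s, essentially the intended 80%. All of this is fair. It is why the power cost is called modest, and the 10% used here is the plan's own allowance.

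On method, a Bonferroni test after one-way ANOVA pools the error over three arms. That gives 59% and 65% rather than 58% and 64%, which changes nothing of substance.

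One practical point stands. Parts of the text are in the past tense, so if enrolment had begun, the true target is a fact to establish before either number is deleted.

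**Conclusion.** The concern holds, with high confidence. The current text contains two incompatible final sample sizes, 30 per arm (90) and 33 per arm (99 implied), and no rule for choosing between them. Each base figure reproduces from its own inputs, so these are two separate calculations and not one calculation misprinted.

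This must be fixed because the planned sample size is wrong in one place or the other. Severity does not rest on lost power, which is about 4 to 5 points unadjusted, or about 6 at 0.05/3, at SD 13.7 s with 10% unreplaced loss, and negligible at SD 8 s. Those figures depend on the assumed two-sided two-sample t-test. The contradiction itself depends on no assumption.

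The misnamed β and the 20% that does not lead to 30 are minor slips that add nothing to severity.

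**What to change.** First confirm with the sponsor which target applies. Then keep one calculation and one number in the Sample size entry, Study Methods items 1 and 2, and Statistical analysis.

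- **If 30 per arm (90):** remove the 33 and state the expected evaluable number (about 27 at 10% loss) with the power it gives under the analysis planned for intubation time, naming the alpha per pairwise comparison. The unadjusted figures (75% for 10 s at SD 13.7 s; 82% for an effect of 0.8) should be printed only if the comparison really is unadjusted; at 0.05/3 they are about 58% and 68%. If the figure is below 80%, say so openly.
- **If 33 per arm (99):** correct the Sample size entry and both Study Methods items.

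In either case:
- If the 10-second calculation is kept, state which SD and formula gave 30 (13.7 s gives 30 by the normal approximation and 31 by the t-test; 8 s gives 11 to 12).
- Say whether lost patients are replaced.
- Replace the stated β of 0.8 with power 0.8 (β 0.2).
- If the calculation from 26 is kept, make the percentage match the number: 26 plus 20% is 31 to 32, and 30 is about 15% above 26.

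**Cost.** Keeping 30 per arm is a wording correction with a restated power and no extra patients, but the alpha for the primary comparison has to be settled first. Choosing 33 needs nine more patients than Study Methods provides for.
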